## **2.7.3 Handling of missing values/censoring/discontinuations**

### **CR rate at Week 13, Week 52 and yearly after**

For the analysis CR, patients who are still ongoing but have not reached the considered timepoint yet will not be included in the analysis of response at that timepoint. Subjects who are not evaluable for response at specific visit for any reason, including missing data and withdrawal from the study before specific visit, will be treated as non-responders in the analysis.

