9.1.4 Early study termination by the sponsor

The study can be terminated by Novartis at any time. This may include reasons related to the benefit/risk assessment of participating in the study, practical reasons (including slow enrollment), or for regulatory or medical reasons.

Reasons for early termination:

- Unexpected, significant, or unacceptable safety risk to participants enrolled in the study;
- Decision based on recommendations from applicable board(s) after review of safety and efficacy data;
- Discontinuation of investigational drug development.

In taking the decision to terminate, Novartis will always consider the participant welfare and safety. Should early termination be necessary, participants must be seen as soon as possible and treated as a prematurely withdrawn participant. The investigator may be informed of additional procedures to be followed in order to ensure that adequate consideration is given to the

protection of the participant's interests. The investigator or sponsor depending on the local regulation will be responsible for informing IRBs/IECs of the early termination of the trial.

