9.2 Study completion and post-study treatment

Study completion is defined as when the last participant finishes her/his Study Completion visit, and any repeat assessments associated with this visit have been documented and followed-up appropriately by the Investigator, or in the event of an early study termination decision, the date of that decision.

All treated participants should have a safety follow-up visit conducted 30 days after last administration of eltrombopag. The information collected is kept as source documentation. All SAEs reported during this time period must be reported as described in [Section 10.1.3](#). Documentation of attempts to contact the participant should be recorded in the source documentation.

The primary analysis will be performed after all participants have completed Week 26 or discontinued prior to Week 26. The primary analysis data will be summarized in the primary clinical study report (CSR). Following the cut-off date for the analysis reported in the primary CSR, the study will remain open. Ongoing participants will continue to receive study treatment and be followed as per the schedule of assessments, as long as participants derive benefit from eltrombopag.

The end of study defined as the earliest occurrence of one of the following:

1. All participants have died or discontinued from the study or complete the study participation per protocol.
2. Another clinical study becomes available that can continue to provide eltrombopag in this participant population and all participants ongoing are eligible to be transferred to that clinical study.

At the end of Year 2 in this study, participants who in the opinion of the Investigator are still deriving clinical benefit from further CsA treatment should be directed by the treating physician to receive the product through commercial channels locally. The final analysis will occur at the end of the study. All available data from all participants up to this cut-off date will be analyzed and summarized in a final CSR.

10 Safety monitoring and reporting

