## **1 Introduction**

This statistical analysis plan (SAP) describes all planned analyses for the clinical study report(s) (CSR) of study CETB115G2201, a non-randomized, open label, multi-center, Phase II study to assess the safety and efficacy of eltrombopag in combination with rabbit anti-thymocyte globulin (r-ATG) and cyclosporine A (CsA) in East-Asian patients with treatment naive severe aplastic anemia (SAA)

[figure not shown]
As specified in Section 12 of the study protocol (version 03 dated 22-Dec-2021), the primary analysis will be performed after all patients have completed Week 26 or discontinued prior to Week 26. Furthermore, a final analysis will be performed at the end of the study. This SAP will also support the final analysis.

The content of this SAP is based on protocol CETB115G2201 version 03 (dated 22-Dec-2021). All decisions regarding analysis, as defined in the SAP document, should be made prior to database lock.

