#### Data included in the analysis

The analysis cut-off date for the primary analysis of study data will be established after all enrolled patients have completed 26 weeks of treatment or have withdrawn prior to Week 26. All statistical analyses will be performed using all data collected in the database up to the data cutoff date. All data with an assessment date or event start date (e.g. vital sign assessment date or start date of an adverse event) prior to or on the cut-off date will be included in the analysis. Any data collected beyond the cut-off date will not be included in the analysis and will not be used for any derivations.

All events with start date before or on the cut-off date and end date after the cut-off date will be reported as 'ongoing'. The same rule will be applied to events starting before or on the cut-off date and not having documented end date. This approach applies, in particular, to adverse event, concomitant medication reports and exposure to eltrombopag. For these events, the end date will not be imputed and therefore will not appear in the listings.

The analysis cutoff date for the final analysis of study data will be established at the end of the study.

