### **Overall response (CR+PR) rate at Week 13, Week 26, Week 52 and yearly after**

Hematologic overall response rate at specific visit is defined as percentage of subjects who achieved hematologic response by investigator assessment at specific visit in FAS.

The overall hematological response is defined as either complete or partial response. CR is defined in [section 2.5.1](#).

Partial response (PR) is defined as blood counts no longer meeting the standard criteria for severe pancytopenia in SAA, equivalent to at least 2 of the 3 criteria below, but are not sufficient for a CR.

- Absolute neutrophil count  $\geq 0.5 \times 10^9/L$
- Platelet count  $\geq 20 \times 10^9/L$
- Reticulocyte count  $\geq 20 \times 10^9/L$

However, improvement in counts that are dependent upon exogenously administered growth factors or transfusion will not be considered as fulfilling response criteria.

The exclusion period of these therapies are detailed below:

- Platelets transfusions: 7 days preceding the assessment of platelet count
- Packed RBC transfusions: 14 days preceding the assessment of hemoglobin
- Growth factors: 21 days preceding the assessment of response.

Of note that the criteria for complete and partial responses must be met on 2 consecutive serial blood count measurements at least one week apart but not more than 4 weeks apart for the Week 13 and Week 26 assessments but only on one blood count measurements for the yearly assessments thereafter.

Patients who relapse or withdraw from the study will be counted and reported as relapsed or withdrawn for all subsequent response assessments. No response (NR) is defined as not fulfilling the response criteria.

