## **2.7.2 Statistical hypothesis, model, and method of analysis**

### **CR rate at Week 13, Week 52 and yearly after**

The number and percentage of subjects who meet the hematological CR criteria (at Week 13, Week 52 and yearly after respectively) will be presented and 2-sided Exact binomial 95% ([Clopper-Pearson](#)) confidence interval will be reported.

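### If Week 52 or later response rates are tabulated at the primary-analysis cut-off, SAP 2.7.3 counts leavers whose visit was not yet due as failures and can bias those rates low

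*SAP*

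**What the plan says.** SAP 2.7.3 handles two groups differently. Its paragraphs on CR rate and on overall response both state that "patients who are still ongoing but have not reached the considered timepoint yet will not be included in the analysis of response" at that timepoint. The next sentence covers everyone who cannot be evaluated, whatever the reason: those with missing data or "withdrawal from the study before specific visit, will be treated as non-responders in the analysis". That sentence does not require that the visit had fallen due by the data cut-off. Death and loss to follow-up are not named, but the general wording takes them in.

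SAP 2.7.1 (overall response) points the same way: "Patients who relapse or withdraw from the study will be counted and reported as relapsed or withdrawn for all subsequent response assessments". It has no due-date condition either.

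On timing, SAP 2.1 places the primary-analysis cut-off after every enrolled patient has completed 26 weeks of treatment or withdrawn earlier. It adds: "All statistical analyses will be performed using all data collected in the database up to the data cutoff date". SAP 2.7.2 says that the CR numbers and percentages "at Week 13, Week 52 and yearly after respectively) will be presented", with exact 95% confidence intervals, and makes no exception for the primary analysis. The introduction notes: "This SAP will also support the final analysis".

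The separate final-analysis SAP (11 November 2024) repeats the clause in its own section 2.7.3. Protocol 12.5.1 says only that missing values and discontinuations are handled much as for the primary endpoint. It has no rule for visits not yet due.

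**The concern.** Take two participants with the same Day 1, neither of whom has reached Week 52 by the cut-off. The one still in the study is left out of both numerator and denominator. The one who has left is added to the denominator as a failure. Among participants not yet due, entry to the table therefore depends on outcome: withdrawal, death or loss brings a person in, and staying in keeps a person out.

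The primary-analysis cut-off is where this can act. By then nobody still ongoing is short of Week 13 or Week 26, so the exclusion sentence can apply only to Week 52 and later.

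At stake is a provisional Week 52 CR or overall response rate, with its exact interval, in the primary study report. No test or stated decision depends on it.

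**Working it through.** **Check of the interval method.** The plan gives no figure for Week 52. Its planning intervals (SAP Table 3-1) reproduce with Clopper-Pearson limits: 14/36 gives 23.1 to 56.5%, 16/36 gives 27.9 to 61.9%, and 18/36 gives 32.9 to 67.1%, with a maximum half-width of 17.1 points.

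**Formula.** Let m be the participants due by the cut-off, R the responders among them, and k those who left before their visit was due. The due-based rate is R/m and the SAP rule gives R/(m+k). For one leaver the drop is R/m − R/(m+1) = (R/m)/(m+1). It is zero when k = 0 or R = 0.

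**How many are due at Week 52.** Inputs:
- three enrolled at 8 December 2020 (Protocol, Amendment 2 status; taken here as the study total);
- 36 enrolled, with last patient first visit on 3 December 2021 (Amendment 3 status);
- cut-off at the last patient's Week 26, allowing 0 to 30 days of screening: 3 December 2021 + 182 days = 3 June 2022, or + 212 days = 3 July 2022.

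Assume N(d) = 3 + 33·t^a, with t = (d − 8 December 2020)/360 and enrolment date taken as Day 1. For linear accrual (a = 1) and the June cut-off, Day 365 is reached by those who started by 4 June 2021. So t = 178/360 = 0.494 and N = 3 + 33 × 0.494 = 19.3.

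| Accrual shape | Day 365 reached (June / July cut-off) | Day 392 passed (June / July cut-off) |
|---|---|---|
| Early-loaded (a = 0.5) | 26.2 / 28.1 | 24.4 / 26.4 |
| Linear (a = 1) | 19.3 / 22.1 | 16.8 / 19.6 |
| Late-loaded (a = 2) | 11.1 / 14.0 | 8.8 / 11.3 |

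These are not firm bounds. Letting earlier participants also lag consent by up to 30 days lowers the linear range to about 17–22. SAP 2.1 sets no latest cut-off, and 1 August 2022 would give about 22–25.

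**Effect of one leaver**, at an assumed Week 52 rate near 45% (the documents give 44% as the expected Month 6 rate only):

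| Due (m) | Due-based rate (exact 95% CI) | With one leaver (exact 95% CI) | (R/m)/(m+1) at 45% |
|---|---|---|---|
| 11 | 5/11 = 45.5% (16.7–76.6) | 5/12 = 41.7% (15.2–72.3) | 3.8 points |
| 20 | 9/20 = 45.0% (23.1–68.5) | 9/21 = 42.9% (21.8–66.0) | 2.1 points |
| 28 | 13/28 = 46.4% (27.5–66.1) | 13/29 = 44.8% (26.4–64.3) | 1.6 points |

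**Average effect.** A simulation of 200,000 trials used three entries at day 0, 33 entries uniform over 360 days, and a cut-off 182 days after that period. Leaving was assumed in 10, 20 or 30% of participants, at times uniform over 364 days. The true rates, with leavers counted as failures, were 39.6, 40.0 and 42.0%. The SAP rule averaged 37.2, 35.4 and 35.2%, which is 2.4, 4.6 and 6.8 points low. A due-by-cut-off denominator recovered the true rates. No not-yet-due leaver occurred in 28, 7 and 2% of trials; in those the bias was zero.

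**Year 2.** The first SAP version is dated 15 September 2020, before the first patient's first visit. Day 672, when the Year 2 window opens, therefore cannot precede 15 September 2020 + 671 days = 18 July 2022. At an earlier cut-off a Year 2 rate would be 0/k, or would have no denominator.

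**The case against.** Four points can be made against this.

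First, the SAP nowhere says outright that Week 52 rates are shown at the primary cut-off. Sections 2.1 and 2.7.2 are general, and the final-analysis SAP will report those rates anyway. This stands, and it makes the point conditional. But section 2.7 of the final-analysis SAP only lists what will not be repeated; it does not remove later timepoints from the primary analysis.

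Second, no document gives a leaving rate, so k is unknown and may be zero. This also stands. A reader might infer that every Week 52 rate at that cut-off is biased low, and the text does not support that. A participant assessed from Day 336 but before Day 365 can also enter early as a responder.

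Third, little depends on these tables. There is no comparator, no formal testing and no formal interim analysis, and Week 52 is estimated again at study end. Leavers may also be visible if they are reported as withdrawn. This keeps the point minor but does not correct the denominator.

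Fourth, a reader might extend the problem to the final analysis, because the clause recurs there and the study can end early: Protocol 9.1.4 says "The study can be terminated by Novartis at any time", and one end-of-study trigger in Protocol 9.2 is that "Another clinical study becomes available that can continue to provide eltrombopag in this participant population". Nothing in the documents indicates an early stop. The last participant's Year 3 visit (Day 1093) falls between 29 November and 29 December 2024, and the Year 3 window would open by about 2 November 2024, before that SAP's date. With full follow-up the clause has essentially nothing to act on.

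One reading would enlarge the effect. 'Ongoing' is not defined. If it means on treatment, or if the relapse rule in 2.7.1 is applied to visits not yet due, then Week 26 non-responders or relapsed participants could also enter early as failures. The documents do not settle this, so no size is claimed for it.

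**Conclusion.** The asymmetry is in the text and its direction is clear. If rates after Week 26 are tabulated at the primary-analysis cut-off, and at least one participant has left before falling due, the rule biases those rates low in expectation. With no such leaver there is no bias.

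The size cannot be fixed from the documents. One leaver costs about 2 points with 20 participants due, and about 1.6 to 3.8 points with 28 down to 11 due. All these shifts lie well inside intervals roughly 40 to 60 points wide. They rest on assumed accrual, an assumed cut-off date and an assumed rate near 45%.

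The Week 26 primary endpoint and the other Week 13 and Week 26 rates are unaffected, because by the cut-off everyone has reached those visits or left. A final analysis after full follow-up is also unaffected. Severity is minor.

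**What to change.** In SAP 2.7.3, replace the sentence on ongoing patients in both paragraphs. For timepoints after Week 26 at the primary-analysis cut-off, include only FAS participants whose Table 2-1 window has closed by the cut-off (Study Day 392 for Week 52), whatever their status. Count the non-evaluable among them as non-responders. 'Ongoing' then needs no definition.

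The alternative is one line saying that Week 52 and later rates are reported only at the final analysis. If a Week 52 rate has already been shown at the primary cut-off, a footnote should give its denominator rule.

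**Cost.** The first option is two sentences and about 2–3 fewer participants in a provisional table (linear accrual: 19.3 − 16.8 = 2.5), some perhaps already assessed on schedule. The interval widens slightly: 8/18 = 44.4% has limits 21.5–69.2%. A limit at Day 372, the protocol's 7-day allowance, would set aside fewer than one participant, but would count a late assessment made after the cut-off as a failure. The second option costs the provisional Week 52 table.

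Changing the final-analysis SAP is optional and for consistency only. If it is changed, the window-end condition should not be carried over to Year 3. That window closes on Day 1148, 55 days after the scheduled visit (1148 − 1093), so it could exclude late entrants who have completed the study.

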### **Overall response (CR+PR) rate at Week 13, Week 26, Week 52 and yearly after**

For the analysis overall response, patients who are still ongoing but have not reached the considered timepoint yet will not be included in the analysis of response at that timepoint. Subjects who are not evaluable for response at specific visit for any reason, including missing data and withdrawal from the study before specific visit, will be treated as non-responders in the analysis.

### **Time to response**

For time to response and time to complete response, if a subject does not meet response/CR before or at the cutoff date, censoring will be performed using the date of the last response assessment.

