Participants who prematurely discontinue eltrombopag will have efficacy assessments at defined time points (Week 13, Week 26, Week 52 and yearly after), unless or until the occurrence of no response at Week 26, relapse or alternative SAA treatment (whichever comes first). Survival and clonal evolution data will be collected for all participants up to Year 3 (Week 156)

4 Rationale

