**Figure 1-1 Study design**

Eligible subjects will be enrolled into the study and will receive eltrombopag (from Day 1 to Week 26) concomitantly with r-ATG (on Days 1-5) and CsA (from Day 1 to Week 26) in the core treatment part.

Efficacy assessments will be performed at Week 13 and Week 26 in the core treatment part of the study.

Participants who are assessed as responders (meeting CR or PR criteria) at Week 26 are eligible to the extension part of the study and continue treatment with eltrombopag and CsA after Week 26.

Study treatment should be discontinued if the participant is not assessed as a responder at Week 26.

During the extension part, eltrombopag treatment will be provided up to Week 52. CsA will be maintained or tapered at the investigator's discretion according to local practice, with a total duration of at least 2 years (18 months after Week 26).

End of treatment assessments will be performed after eltrombopag discontinuation anytime during the study. After that, safety follow-up visit will be performed 30 days after the discontinuation of eltrombopag, and participants will enter the long-term follow-up part, with yearly efficacy and clonal evolution assessments up to Year 3 (Week 156).

For non-responders at Week 26, and participants who relapse or receive alternative SAA treatment, safety follow-up visit will be performed 30 days after the discontinuation of eltrombopag, and then clonal evolution and survival will continue to be followed up to Year 3 (Week 156).

Participants who prematurely discontinue eltrombopag will have efficacy assessments at defined time points (Week 13, Week 26, Week 52 and yearly after), unless or until the occurrence of no response at Week 26, relapse or alternative SAA treatment (whichever comes first). Survival and clonal evolution data will be collected for all participants up to Year 3 (Week 156).

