### **Time to response**

Time to response is defined as the time from the date of the start of study treatment until the first documented and confirmed response (either CR or PR) per programmatically derived.

Time to complete response is similarly defined as the time from the date of the start of study treatment until the first documented complete response.

All subjects in the FAS will be included in the time to response/CR calculations.

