### **Time to response**

The Kaplan-Meier curve of the time to response and time to complete response will be constructed, and the quartiles of the survival function will be provided along with 95% confidence interval. Kaplan-Meier estimates with 95% confidence intervals every 3 months will be summarized as well.

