### **5.4.2 Secondary analysis**

#### **Kaplan-Meier estimates**

For time to event endpoints (time to response, duration of response etc.), an estimate of the survival function will be constructed using Kaplan-Meier (product-limit) method as implemented in PROC LIFETEST with METHOD=KM option.

Quartiles of the survival function, if reached, will be obtained along with 95% confidence intervals calculated from PROC LIFETEST output using the method of ([Brookmeyer and Crowley, 1982](#)). Kaplan-Meier estimates of the survival function with 95% confidence intervals at specific time points will be summarized. The standard error of the Kaplan-Meier estimate will be calculated using Greenwood's formula ([Collett, 1994](#)).

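### Kaplan-Meier for time to complete response carries the partial responders' late CR rate over to Week 26 non-responders, so estimates after Week 26 overstate the incidence of CR whenever late CRs occur

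*SAP*

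**What the plan says.** The SAP file holds two plans: the primary-analysis SAP (last updated 1-Jul-2022) and the final-analysis SAP (11-Nov-2024). The point concerns the first.

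- **Population** (2.7.1, Time to response): "All subjects in the FAS will be included in the time to response/CR calculations".
- **Estimator** (2.7.2): "The Kaplan-Meier curve of the time to response and time to complete response will be constructed", with quartiles, and "Kaplan-Meier estimates with 95% confidence intervals every 3 months will be summarized as well". Section 5.4.2 confirms the product-limit method, with Brookmeyer-Crowley intervals for quartiles and Greenwood standard errors.
- **Censoring** (2.7.3): for anyone without response or CR by the cut-off, "censoring will be performed using the date of the last response assessment". Death, no response at Week 26 and alternative SAA treatment get no separate handling. Deaths are not named, but the rule covers them.
- **Treatment after Week 26** (SAP 1.1): "Study treatment should be discontinued if the participant is not assessed as a responder at Week 26".
- **Efficacy assessment** (Protocol Section 3, repeated in SAP 1.1) continues "unless or until the occurrence of no response at Week 26, relapse or alternative SAA treatment (whichever comes first".
- **Status**: Section 4 lists time to response among the endpoints added beyond the protocol. Section 2.7 of the final-analysis SAP says it will not be reproduced.

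**The concern.** Kaplan-Meier censoring assumes that a censored participant would go on to the event at the same rate as those still followed. Here participants leave because their outcome was poor: they died, moved to another SAA treatment, or had not responded at Week 26. The last group is the largest by design. Its members are taken off study treatment and no longer assessed for response, while partial responders stay under assessment and may convert to CR. After Week 26 the observed conversion rate is therefore that of partial responders, and the product-limit estimate applies it to non-responders as well.

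At stake are the month 9 and month 12 estimates of time to CR, and the quartiles. A median time to CR could be reported although fewer than half of the participants ever reached CR. The error runs in one direction, in favour of the treatment.

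**Working it through.** **The plan's own figures.** The SAP gives no figure for time to response. Its only design figures are the exact intervals for the CR rate with N = 36 (Table 3-1). These reproduce: 14/36 (23.1, 56.5), 16/36 (27.9, 61.9), 18/36 (32.9, 67.1), with a maximum half-width of 17.08%, stated as 17.1%.

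**Set-up.** At Week 26 let there be c CRs, p partial responders and m non-responders, with c + p + m = 36. Let k of the p partial responders reach CR by Week 52. Assume no deaths or dropout, full follow-up, and that CRs at Week 26 are counted before the censoring at Week 26.

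- As planned: 1 − KM = 1 − [(p + m)/36] × [1 − k/p]
- Cumulative incidence, with the m non-responders as a competing event: (c + k)/36
- Difference: (m × k)/(36 × p)

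The difference is zero when k = 0. It grows with the number of non-responders per partial responder.

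**Inputs.** k is not given in the documents and is assumed throughout. The 14/10/12 split is also assumed. The other two rows take c = 16 from the SAP's expected CR rate (44.0% × 36 = 15.8). They take total responders from Protocol 1.1: 57.1% in the Japanese r-ATG study, which was 4 of 7 participants (57.1% × 36 = 20.6, so 21), and 70%, the top of the range cited for Asian studies (25.2, so 25).

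| CR / PR / NR at Week 26 | Late CRs | 1 − KM, Week 52 | Cumulative incidence | Excess (points) |
|---|---|---|---|---|
| 14 / 10 / 12 | 2 | 1 − (22/36)(8/10) = 51.1% | 16/36 = 44.4% | 6.7 |
| 14 / 10 / 12 | 4 | 1 − (22/36)(6/10) = 63.3% | 18/36 = 50.0% | 13.3 |
| 16 / 9 / 11 | 1 | 50.6% | 47.2% | 3.4 |
| 16 / 9 / 11 | 4 | 69.1% | 55.6% | 13.6 |
| 16 / 5 / 15 | 1 | 55.6% | 47.2% | 8.3 |
| 16 / 5 / 15 | 4 | 88.9% | 55.6% | 33.3 |

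In the first row the Kaplan-Meier curve crosses 50%, so a median time to CR would be reported with 16 of 36 in CR.

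**Staggered follow-up.** Take 16 / 5 / 15, with two partial responders administratively censored at Week 39 and one CR among the remaining three at Week 52. Kaplan-Meier gives 1 − (20/36)(2/3) = 63.0%. Cumulative incidence gives 16/36 + (5/36)(1/3) = 49.1%.

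**Time to any response.** With 21 responders by Week 26 and no earlier losses, both methods give 21/36 = 58.3%. The non-responders censored at Week 26 are nearly everyone still at risk, and nobody left under assessment supplies a later response rate to extrapolate. Only earlier losses matter. With 1, 2 or 3 deaths before any response assessment (an assumption), Kaplan-Meier gives 21/35 = 60.0%, 21/34 = 61.8% or 21/33 = 63.6%. The same deaths move CR at Week 26 (16/36 = 44.4%) to 45.7%, 47.1% or 48.5%. These figures censor the deaths at time 0. The SAP sets no date for a participant who dies before the first response assessment.

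**The case against.** The other side has real points.

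- **The size is assumed.** The documents give neither the number of late CRs nor the number of early deaths. This stands: the table shows what could happen and does not forecast it.
- **Follow-up at the primary cut-off is partial.** The cut-off comes once all participants have reached Week 26 or withdrawn (SAP 2.1). The last first visit was on 03-Dec-2021 and only three participants were enrolled by 08-Dec-2020, so many partial responders may not have reached Week 52. This stands against reading the full-follow-up figures literally. It does not remove the bias, as the staggered case shows.
- **Little depends on the endpoint.** It is supportive, the study is single-arm, and no formal test is planned. The Week 26 CR rate and the visit-based rates count non-evaluable participants as non-responders. This stands and limits the weight of the point.

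Three stronger readings are tempting, and the documents do not support them.

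- A reader might infer that censoring the Week 26 non-responders also inflates time to any response. It does not, for the reason shown in the working.
- A reader might infer that the estimates must exceed the share of participants who could reach CR. With 14 / 10 / 12 and four late CRs, 63.3% lies below 24/36 = 66.7%. What is exceeded is the cumulative incidence. Other assumed counts can pass the ceiling (16 / 5 / 15 with two late CRs gives 66.7% against 21/36 = 58.3%), but that is not a general result.
- A reader might take a gap between the 12-month estimate and the Week 52 CR rate as proof of bias. The two differ by construction: the visit rate is cross-sectional and investigator-assessed, and leaves out ongoing participants who have not reached the visit. Time to response is a first event, derived from laboratory data. Some gap would remain under any estimator.

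**Conclusion.** The concern holds for time to CR after Week 26 in the primary-analysis SAP. Once any partial responder reaches CR after Week 26, Kaplan-Meier overstates the cumulative incidence of CR at months 9 and 12 and distorts the quartiles. In the 14 / 10 / 12 illustration the excess is about 7 to 13 points for two to four late CRs. With counts anchored on the documents' response rates and one to four late CRs, it runs from about 3 to 33 points. It is zero if no CR occurs after Week 26 and nobody dies or drops out before it.

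Time to any response is exposed only through deaths or alternative treatment before response. For one to three assumed early deaths that is about 2 to 5 points.

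The primary endpoint and the visit-based CR and overall response rates are unaffected. The change is worth making because the error is one-directional, the endpoint was added to support the efficacy case in a bridging study for registration, and the final analysis will not revisit it.

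**What to change.** In SAP 2.7.2, 2.7.3 and 5.4.2, replace Kaplan-Meier for these two endpoints with the Aalen-Johansen cumulative incidence:

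- **Competing events for response and for CR:** death and alternative SAA treatment.
- **Additional competing event for CR:** end of efficacy follow-up because of no response at Week 26.
- **Censoring:** only administrative cut-off and true loss to follow-up.
- **Intervals:** replace the Brookmeyer-Crowley quartile intervals and Greenwood standard errors for these endpoints with methods suited to cumulative incidence. Report a quartile only if the cumulative incidence reaches it.

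The text should also say how relapse from partial response before CR is classified, because the protocol ends efficacy assessment there too.

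The cost is SAP wording and a small programming change in the same SAS procedure. No new data are needed. The estimates will be less favourable than those from the planned method. If the primary analysis has already been reported, the same data can be re-analysed as a supplement.
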